2.3 Study Design

The study is designed as operationally seamless to facilitate the updating of the thresholds on the Receiver Operating Characteristic (ROC) curves for swallowing safety if required and to validate the DDS classifier with a fixed threshold using an independent validation set. The threshold updating will carried out separately for each of the three consistencies.

PORSCHE trial will start with the frozen classifiers based on fixed thresholds derived using ROC analysis from the completed exploratory trial (Protocol 11.48.CLI). The trial will initially start as a 3-look group sequential design (GSD). At the first interim, sensitivities and specificities will be calculated based on the fixed thresholds. If the Area under the ROC curves at the first interim is above 75% but the corresponding sensitivity and/or specificity are low then the threshold will be revised based on the first interim data. In this case, the validation will exclude the data used for the first interim, i.e. the validation trial will start with the first patient enrolled after the first interim analysis data cut-off date and will be carried out as a 2-look GSD. In case the fixed thresholds from the completed exploratory trial data are not revised using the first interim data, the trial will continue as planned.

The study design in summarized in Figure 2-1.

Figure 2-1: Trial Design

2.4 Efficacy Assessments

2.4.1 Primary Efficacy Endpoint

The primary efficacy of the DDS will be measured as the sensitivity and specificity obtained from comparing the DDS predicted swallow safety outcome at the subject level (from up to 4 boluses) with the clinical reference standard VFSS swallow safety outcome (binary) for THIN-Ba boluses.

Swallowing safety describes risk of penetration-aspiration which describes impaired airway protection. The impaired swallowing safety is defined as $PAS \ge 3$ as determined by VFSS. (The PAS - Pentration Aspiration Scale – is provided in the Appendix B of the Protocol)

2.4.2 Secondary Efficacy Endpoints

At the final analysis, if the primary endpoint meets statistical significance then formal testing and analysis for the following secondary endpoints will be carried out in a hierarchical fashion in the specified order:

- 1. Sensitivity and specificity of detecting impaired swallow safety using MILD-Ba boluses (up to 3 boluses per subject).
- 2. The sensitivity and specificity of detecting impaired swallow safety using MOD-Ba boluses (up to 3 boluses per subject).
- 3. The DDS algorithm is also capable of detecting impaired swallow efficiency. The sensitivity and specificity of detecting impaired swallow efficiency using THIN-Ba boluses (up to 4 boluses per subject).
- 4. Sensitivity and specificity of detecting impaired swallow efficiency using MILD-Ba boluses (up to 3 boluses per subject).
- 5. The sensitivity and specificity of detecting impaired swallow efficiency using MOD-Ba boluses (up to 3 boluses per subject).

The success criteria for the primary and each of the secondary endpoints will be the same as specified in Section 3.1.

2.4.3 Exploratory Endpoints

The analysis on the following tertiary endpoints will be considered as exploratory:

• Prevalence of boluses resulting in "grey" outcomes of the classifier for safety and efficiency of the swallows on thin (THIN-Ba) and thickened stimuli (MILD-Ba and MOD-Ba)

- Prevalence of impaired swallowing safety and efficiency of swallows of thin (THIN-Ba) and thickened stimuli (MILD-Ba and MOD-Ba) as determined by VFSS at bolus and patient levels.
- Positive and Negative predictive value (PPV and NPV) of detecting swallow safety and efficiency problems using DDS and using THIN-Ba, MILD-Ba and MOD-Ba stimuli.
- Prevalence of impaired swallowing safety and efficiency of the swallows of thin (THIN-Ba) and thickened stimuli as determined by VFSS at bolus and patient level by the following predetermined subgroups: stroke, other neurological diseases, other patients.
- Timing and Outcome of the dysphagia screening as per usual care protocol of the study site
- Timing and Outcome of the dysphagia Clinical Swallow Assessment (CSE) by speech language pathologist (SLP) where applicable as per usual care protocol of the study site
- DDS accuracy in terms of AUC by sub-group (Stroke, Other Neurological Diseases and Others) for swallow safety and efficiency problems for all consistencies (THIN-Ba, MILD-Ba, MOD-Ba).
- Impact (or association of) of VFSS results on Nutritional Management.

2.5 Safety Endpoints

All adverse events (AEs) will be observed from the time the consent form is signed through the exit of the subject from the study.

3 Statistical methodology

3.1 Success Criteria and Hypothesis Testing

The success criteria for the DDS device validation trial is that the sensitivity is greater than 80% with a specificity greater than 50%. The sensitivity and the specificity will be estimated using an independent validation dataset. The following one-sided hypothesis testing will be carried out:

$$H_0 : H_0^{se} \cup H_0^{sp} \text{ vs.}$$

$$H_A : H_A^{se} \cap H_A^{sp},$$
(1)

where,

 $\begin{array}{lll} H_0^{se} & : & \mathrm{Sensitivity} \leq .8, \\ H_A^{se} & : & \mathrm{Sensitivity} > .8, \\ H_0^{sp} & : & \mathrm{Specificity} \leq .5, \text{ and} \\ H_A^{sp} & : & \mathrm{Specificity} > .5. \end{array}$

Each of H_0^{se} vs. H_A^{se} and H_0^{sp} vs. H_A^{sp} will be tested at one-sided 2.5% level of significance which will (conservatively) preserve the over-all type-I error for testing H_0 vs. H_A .

The same hypothesis test as in (1) will be applied to the secondary endpoints. Hypothesis will be carried out in a hierarchical fashion to ensure that the type-I error is controlled at the one-sided 2.5% level.

3.2 Determination of Sample Size

The power and the sample size to test the hypothesis depends on several unknown parameters:

- 1. Subject level prevalence;
- 2. The prevalence of impaired swallows conditional on subject having Dysphagia;
- 3. The true sensitivity and specificity of the DDS device in detecting swallow impairment; and
- 4. The optimum threshold on the ROC curve.

Based on estimates from the exploratory study data, if the DDS is assumed to have a sensitivity and specificity of at least 86% and 60% respectively and approximately 35% patients show impaired safety, then a power of 90% to test H_0 vs. H_A (from equation (1)) can be achieved with 700 to 800 subjects under a fixed design. Considering that data from additional 100 to 200 subjects may be used for threshold calibration, the starting sample size is 900 subjects. A sample size re-estimation will be carried out at the last interim analysis. The maximum sample size is set to 1300 (see Table 5-2).

3.3 Group Sequential Design (GSD)

The clinical trial will initially start as a 3-look GSD. Alpha-spending will be calculated using Lan-DeMets spending function with O'Brien-Fleming parameter (LDOF) [2]. At the first interim analysis (IA-1) the threshold on the ROC curve may be re-computed using the ROC curve generated using the IA-1 data, in which case, the validation trial would start afresh following IA-1 using a 2-look GSD. Data included in the IA-1 would no longer be used for the validation phase. If the threshold is not re-computed at the first interim and the efficacy boundary has not been crossed then the trial continues as planned as a 3-look GSD.

3.4 Timing of Interim Analysis-1

The overall subject-level prevalence of impaired safety and efficiency as determined by the central lab VFS reading will be continuously monitored in a blinded fashion, i.e. the study staff will be blinded to the DDS results. The first interim analysis will be performed when the prevalence can be estimated using a 95% confidence interval of width no more than 15%. Thus if the true (subject-level) prevalence is 20% then the interim analysis may be carried out after 110 subjects. On the other hand if the prevalence is around 50% then around 170 subjects would be needed. If the monitoring is carried out after every 50 subjects have completed the study, the first interim will be carried out around completion by 200 subjects.

3.5 Group Sequential Design and Sample Size Re-estimation Details

Due to uncertainties about the population parameters and their influence on the power, an adaptive sample size re-estimation (SSR) is proposed. This is after the first interim the trial continues as a 3-look GSD with out changing the threshold then a SSR would be done at the second interim analysis while if the threshold is changed at the first interim then the SSR will be carried out at the only interim analysis time for the freshly started validation trial post threshold re-calibration. The following adaptation rules will be applied:

- 1. If the threshold is changed based on the first interim look, then a new appropriately powered (80%-90%) 2-look group sequential design trial will be started. The powering will be based on the sensitivity and specificity estimates obtained at the first interim. The interim and the final analysis for this new trial would not include the data from subjects included in the first interim analysis.
- 2. At the interim of the new validation trial, unless the interim Z statistic crossed the efficacy boundary, a sample size re-estimation based on conditional power being in the promising zone [1] will be carried out. Conditional power (CP) will be calculated both for sensitivity as well as specificity. Promising zone is defined as both the CPs are between 50% and 90%. Futility may also be decided in case of low conditional power for either sensitivity or specificity.
- 3. The increase will be determined equating CP to the desired power of 90%. This will be bracketed by a minimum increase of 50 subjects and max increase defined by the maximum sample size of 1300.
- 4. In case the threshold is not changed at the first interim, the trial continues as a 3-look GSD and the SSR adaptation rules in 2-3 above will apply at the second interim look.

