The trial will start with the frozen classifier based on a fixed threshold derived using ROC curve from the completed exploratory trial. The clinical trial will initially start as a 3-look group sequential design (GSD). At the first interim, sensitivity and specificity will be calculated based on the fixed threshold. If the Area under the ROC curve at the first interim is above 75% but the sensitivity and/or specificity are low then the threshold will be revised based on the first interim data. In this case, the validation will exclude the data used for the first interim, i.e. the validation trial will start with the first patient enrolled after the first interim analysis data cut-off date. In case the fixed threshold from the completed exploratory trial data is not revised using the first interim data, the trial continues as planned. At the last interim analysis a sample-size re-estimation wil be carried out in order to compensate for design parameters like accuracy and prevalence that may be slightly different from the values assumed during trial design.

If the classifier cannot analyze the signal (e.g. due to signal-to-noise level), it will result in a "grey" outcome of the classifiers. The prevalence of "grey" outcomes among analyzed boluses for safety and efficiency classifier on thin (THIN-Ba) and thickened stimuli (MILD-Ba and MOD-Ba) at site level will be monitored centrally during the trial.

Blinding:

VFSS analysis, considered in this study as the clinical reference method (gold standard), will be performed by an independent and central VFSS assessment laboratory which will be blinded to the DDS results. The interim analyses will be carried out in an unblinded fashion by an independent statistical center (iSC) while the interim decisions will be made by an independent data monitoring committee (iDMC). The iDMC will also monitor the prevalence of swallow safety problems in a blinded manner throughout the course of the Trial.

Procedure:

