3.11.2 IA-2 (or IA- 1^n)

- 1. Test primary and secondary efficacy hypotheses in the pre-specified hierarchy. If efficacy boundaries for the primary and the first two secondary endpoints are crossed then the trial may be stopped early and the final analysis is planned with the overruns
- 2. If the efficacy boundaries for the primary endpoint and the first two secondary endpoints (i.e. for sensitivities and specificities for detecting impaired safety with Thin-BA, Mild-BA and Moderate-BA) are not crossed then consider sample size re-estimation (SSR) using the promising zone approach (Mehta and Pocock, 2011, Statistics in Medicine).
 - Calculate conditional power (CP) for sensitivities and specificities for the primary efficacy (Thin-safety). If $0.5 \leq CP \leq 0.9$ then increase sample size to meet CP = 0.9 up to a maximum of 1300 subjects overall (including the IA-1 subjects)
 - If CP < 0.5 or CP > 0.9 then the trial continues as planned.
 - If CP < 0.2 then consider futility

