0.35	0.85	0.65	0.74	0.625	0.258	525	1091	1300
0.45	0.85	0.65	0.65	0.741	0.406	525	1100	1300
0.55	0.85	0.65	0.57	0.829	0.538	525	1105	1300
0.65	0.85	0.65	0.48	0.881	0.614	525	1103	1300
0.35	0.92	0.55	0.56	0.705	0.342	525	1082	1300
0.45	0.92	0.55	0.62	0.647	0.275	525	1079	1300
0.55	0.92	0.55	0.64	0.580	0.192	525	1070	1300
0.65	0.92	0.55	0.63	0.481	0.098	876	1054	1300
0.35	0.92	0.58	0.41	0.969	0.828	525	1026	1300
0.45	0.92	0.58	0.46	0.941	0.803	250	1050	1300
0.55	0.92	0.58	0.50	0.908	0.734	525	1080	1300
0.65	0.92	0.58	0.54	0.836	0.580	525	1089	1300

Table 5-2: Simulation results under the Intersection Alternate Hypothesis for proposed group sequential design with thresholding at interim-1 and SSR at the last interim, for varying prevalence, sensitivity and specificity.

Prev.: Data generating prevalence

Se: Data generating Sensitivity

Sp: Data generating Specificity

Prop ChangeTH: Proportion of runs where threshold was changed at IA-1

Overall Power: Power to detect at least the primary hypothesis

Min.N, Avg.N, Max.N: All calculated over 10,000 $\,$

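### SAP 3.5 increases N only if both conditional powers lie in 50–90%, while SAP 3.11.2 applies the limits to one undefined CP; at the planning values the 3.5 rule almost never fires

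*SAP*

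**What the plan says.** SAP 3.5 item 2 has CP calculated for sensitivity and for specificity and then says "Promising zone is defined as both the CPs are between 50% and 90" per cent. Item 3 sizes the increase to bring CP to 90%, with at least 50 extra subjects and a maximum of 1,300. Item 4 applies items 2 and 3 at the second interim (IA-2) when the threshold has not been changed.

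SAP 3.11.2 also asks for CP for sensitivities and specificities of the primary endpoint, but each rule that follows uses one CP. If it lies from 0.5 to 0.9, "then increase sample size to meet CP = 0.9 up to a maximum of 1300 subjects overall". Otherwise, "If CP < 0.5 or CP > 0.9 then the trial continues as planned". It does not repeat the 50-subject minimum.

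The Protocol Synopsis (Trial Design) gives the purpose of the re-estimation: "in order to compensate for design parameters like accuracy and prevalence that may be slightly different from the values assumed during trial design".

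**The concern.** The CP in 3.11.2 can be read as each, either, the smaller, or both. Neither section says explicitly what happens when one CP is in the zone and the other is above 0.9. At the planning values, that is the usual situation whenever the sensitivity CP is in the zone.

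Read literally, 3.5 resolves this case against its own purpose. SAP 3.7 requires both Z statistics to cross, so an under-powered sensitivity test sinks the trial however good specificity looks. A high specificity CP nevertheless takes the trial out of the zone and N stays where it was.

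The adaptation uses unblinded data, so the rule has to be fixed before those data are seen. Tables 5-1 and 5-2 support type I error and power only for the rule that was coded.

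**Working it through.** **Inputs from the documents.** One-sided 2.5% for each of sensitivity and specificity, null values .80 and .50 (SAP 3.1). Planning values .86 and .60, prevalence .35, starting N 900, maximum 1,300 (SAP 3.2). First interim at about 200 (SAP 3.4). Lan-DeMets O'Brien-Fleming spending (SAP 3.3) and the Z statistics of SAP 3.7.

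**Assumptions.** The SAP text gives neither the IA-2 time nor the effect under which CP is calculated. IA-2 is taken at 450–675 and CP under the observed trend. The original final bound is kept after an increase. Only the primary endpoint is simulated.

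**Planned power.** SAP 3.2 states 90% power at 700–800 subjects, fixed design, "if the DDS is assumed to have a sensitivity and specificity of at least 86% and 60% respectively". With power = Φ[((p1−p0)√n − 1.96√(p0(1−p0))) / √(p1(1−p1))]:
- N = 700 (245 impaired, 455 unimpaired): sensitivity Φ[(.06√245 − .784)/.347] = .673, specificity .991, product .666.
- N = 800 (280 and 520): .737, .996, product .734.

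The 90% is not reproduced. That is a separate point, but it shows that sensitivity is the limiting endpoint.

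**Worked example, IA-2 at 525 of 900.** There are 184 impaired and 341 unimpaired subjects; about 315 and 585 are expected at 900. The bounds at 200/525/900 are 4.613/2.713/1.978. With n1 subjects at the interim, n2 at the end and final bound c,

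CP = Φ[(Z·n2/√n1 − c√n2) / √(n2 − n1)].

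- Sensitivity 158/184: Z = 1.990, CP = .835.
- Specificity 191/341: Z = 2.220, CP = .925. Not both in the zone, so 3.5 leaves N at 900.
- Specificity 190/341: Z = 2.112, CP = .889. Both in the zone, so 3.5 raises N until the sensitivity CP reaches .90, at about 1,126.

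One fewer correct call adds 226 subjects. With 3.11.2 read on the smaller CP, N goes to about 1,126 in both cases.

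**How often N is increased** (.86/.60, prevalence .35, 200,000 runs per setting, share of all trials):

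| IA-2 at | Both CPs in zone (3.5) | Smaller CP in zone | Either CP in zone |
|---|---|---|---|
| 450 | 1.6% | 30% | 32% |
| 525 | 1.2% | 29% | 30% |
| 600 | 0.8% | 27% | 28% |
| 675 | 0.5% | 24% | 25% |

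The specificity CP exceeds .9 in 92–97% of trials. In about 23–26% of all trials the sensitivity CP is in the zone and the increase is blocked for that reason. A second simulation gave 1.65% at 450 and 0.6% at 650 for the 3.5 rule. Restricted to trials whose threshold was not changed, it gave 0.35–1.7%.

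**Power at IA-2 525.** No re-estimation .786, 3.5 rule .787, smaller-CP rule .816.

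**Other settings.**
- Restarted trial of 700 with interim at 350: 3.5 rule 3.2%, smaller CP 31%.
- Specificity .55: the specificity CP exceeds .9 in only 38%, and the three readings fire in 6.7%, 29% and 45%.
- CP under the design trend: 3.5 rule 0.1–0.2%, smaller CP 30–49%.
- Looks at 250/525/876, suggested by the Min.N columns: 1.2% and 29%, power .776 and .805.

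**Table 5-2, row prevalence .65, Se .85, Sp .65.** The threshold changed in 48% of runs and Avg.N is 1,103. Suppose every restart ran to 1,300, no unrestarted trial was increased and none stopped early. Then Avg.N is at most
- 0.52 × 876 + 0.48 × 1,300 = 1,080 (base 876, the Min.N in Table 5-1), or
- 0.515 × 900 + 0.485 × 1,300 = 1,094 (base 900, and 48% taken as 48.5% before rounding).

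Reaching 1,103 needs 9/(0.515 × 400) = 4% to 23/(0.52 × 424) = 10–11% of unrestarted trials increased to the cap. In this row the 3.5 rule fires in about 0.4–0.5% of trials, under 1% of unrestarted ones.

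**The case against.** The strongest reply is that 3.11.2 is incomplete rather than contradictory. The zone is defined once, in 3.5, with both used for the zone and either for futility, which looks deliberate. The single-CP sentence in 3.11.2 can be read to agree: if one CP exceeds .9, continue. The missing 50-subject minimum is covered by 3.5. This stands as far as it goes, but nothing in 3.11.2 fixes that reading, and if it is the intended one, the rule that almost never helps sensitivity is the operative rule.

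The effect also depends on the scenario. At .90/.60, near the performance the amendment log says is targeted, power is .9973 under the 3.5 rule and .9976 under the smaller-CP rule, so the choice hardly matters there. It does matter at .86/.60, the values on which SAP 3.2 bases the sample size. The gain of about 3 points is modest.

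Any zone with cut-offs produces jumps, including one on the smaller CP. That is true, but a jump caused by the stronger endpoint's success is a different defect.

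The Table 5-2 argument rests on one row and an inferred base N. With base 900 the gap is 9 subjects, and it closes if unrestarted trials were coded at about 918. It supports a question to the sponsor, not a finding that the tables are wrong. Figures 2-1 and 5-1 were not available for this check and may show the IA-2 timing or how the CPs combine; the text should then agree with them.

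**Conclusion.** The concern holds and should be fixed. The two sections do not give one unambiguous rule for the pair of CPs. The explicit one, in 3.5, withholds the increase when sensitivity needs it and specificity is strong. The rarity of the increase rests on the assumed IA-2 time and observed-trend CP, on a primary-endpoint-only model without the SAP's extra stopping condition on two secondary endpoints, and on the planning values. Design-trend CP makes the increase rarer still; a specificity of .55 makes it more frequent. Confidence is high on the wording and on the size under these assumptions, and lower on which rule was simulated for Table 5-2.

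**What to change.** In SAP 3.5 item 2 and in 3.11.2, define the zone on the smaller of the two CPs:
- If 0.5 ≤ min(CP_se, CP_sp) ≤ 0.9, increase N until the smaller CP reaches 0.9, by at least 50 subjects and to at most 1,300 overall.
- Continue as planned only if the smaller CP is below 0.5 or both exceed 0.9.

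State the IA-2 timing and the trend used for CP. State which rule produced Tables 5-1 and 5-2, and rerun them if it differs from the final text.

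The cost is SAP wording plus a possible simulation rerun. Against the literal 3.5 rule, average N rises by about 80–95 subjects within the existing cap. Type I error with the smaller-CP rule was .018–.024 in eight null settings (Se/Sp .80/.60, .80/.65, .90/.50 and .86/.50, at prevalence .35 and .65, looks at 200/525/900). This change does not restore the 90% power stated in SAP 3.2.

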3.6 Final Analysis in case of Early Stopping

If the decision is taken to terminate the study at one of the two planned interim analysis the study will enter a closeout phase. During this phase, which extends from the soft database lock prior to the interim analysis iDMC meeting until the final database lock, additional data will arrive. The final analysis, being based on the totality of evidence, will include these additional data, resulting in an increase in the information fraction from what it was at the time of the interim analysis. The significance level for the formal hypothesis testing at the final analysis will then be recomputed from the LDOF spending function at the new information fraction. Details of this will be provided in the SAP which will be finalized and issued before the first interim analysis.

3.7 Efficacy Analysis

Efficacy of the DDS screening device will be established if it's accuracy in terms of sensitivity and specificity with respect to VFSS to detect swallowing safety impairment are high, in particular, sensitivity has to be higher than 80% while the specificity has to be higher than 50%. The hypothesis test in equation (1) in Section 3.1 is to be tested for the primary endpoint hypothesis regarding the sensitivity and specificity using Thin-BA boluses as well as for secondary endpoints listed in Section 2.4.2. The secondary endpoint s will be tested in a hierarchical fashion if and only if the primary endpoint meets statistical significance. The hypothesis testing for primary and secondary endpoint will be carried out using the following test statistics

$$Z_{se} = \sqrt{N_d} \frac{\widehat{SE} - SE_0}{\sqrt{SE_0(1 - SE_0)}}; \text{ and}$$
$$Z_{sp} = \sqrt{N_h} \frac{\widehat{SP} - SP_0}{\sqrt{SP_0(1 - SP_0)}},$$

where N_d and N_h are the number of diseased and healthy subjects in the analysis dataset, $SE_0 = .8$ and $SP_0 = .5$. N_d and N_h will be determined solely based on the VFSS (gold-standard) results.

At each interim the above test statistics for sensitivity and specificity will be computed and the compared to the group-sequential boundary derived using the LDOF alpha-spending function separately for sensitivity and specificity. Thus the primary efficacy hypothesis will meet statistical significance if both Z_{se} and Z_{sp} cross their corresponding efficacy boundaries. If the primary endpoint sensitivity and specificity cross their corresponding boundaries then the secondary endpoints using the same test-statistics will be tested in the pre-specified hierarchy specified in Section 2.4.2. Note that group sequential boundaries are non-binding.

